7.5.2 Clinical Laboratory Evaluations

Clinical laboratory evaluations (including hematology and serum chemistry) will be summarized for each visit using descriptive statistics. Change from baseline will also be summarized. As a baseline the last assessment before the first day of MDV3100 intake from the prior study will be used. Shift analysis tables will present shift from baseline to the same visits using the NCI-CTCAE grade and laboratory reference range indicator. All clinically significant abnormal laboratory values will be recorded as AEs and graded using NCI-CTCAE guidelines.

Laboratory data will be listed for each test. Each laboratory result will be flagged as low (L), normal, or high (H) at each visit according to laboratory reference ranges. In addition a listing will be presented with the indicated subset of laboratory parameters, if at least one of the following criteria is fulfilled: ALT or AST \geq 3xULN or Bilirubin \geq 2.0 mg/dL (34.2 μ mol/L) or Creatinine $>$ 352 μ mol/L (4.0 mg/dL).

7.5.3 Physical Examination

All clinically significant abnormal findings will be recorded as medical history or AEs and graded using NCI-CTCAE guidelines.

7.5.4 Vital Signs

Descriptive statistics will be presented for each vital sign measurement at each visit. Change from baseline will also be summarized. In addition for weight a frequency table indicating percentage change from baseline by category* will be provided. As a baseline the last assessment before the first day of MDV3100 intake from the prior study will be used.

Vital signs data will be provided in a data listing.

*The percentage change will be categorized in 7 different categories, from loss >=20% up to gain >=20% (see TLF specifications for the other categories)

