3.4 Discontinuation Criteria for Individual Subjects

A discontinuation is a subject who enrolled in the study and for whom study drug is terminated for any reason.

The subject is free to withdraw from the study treatment and/or study for any reason and at any time without giving reason for doing so and without penalty or prejudice. The investigator is also free to terminate a subject's involvement in the study at any time if the subject's clinical condition warrants it.

Subjects will be discontinued from study drug when continued administration of study drug is deemed to be not in the subject's best interest by the investigator based on clinical assessments. Use of other investigational drugs will also lead to discontinuation. It is also possible that the sponsor or the competent authorities (CA) request termination of the study if there are concerns about conduct or safety.

Unless the subject withdraws consent, all subjects discontinuing study drug for any reason will have a safety follow-up visit 30 days after their last dose of MDV3100. For subjects who enroll into Study [REDACTED], a safety follow-up visit is not required. For these subjects, the final visit for Study 9785-CL-0121 will serve as Day 1 for Study [REDACTED] (± 7 days).

Individual subjects may discontinue the study in case of:

1. Not fulfilling inclusion or exclusion criteria
2. Adverse event
3. Lack of efficacy
4. Withdrawal of consent
5. Subject lost to follow-up
6. Protocol violation.

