7.5.5 Electrocardiogram (ECG)

Overall ECG interpretation will be summarized for each visit. A shift analysis table showing shifts from baseline to each visit in overall ECG interpretation (normal, abnormal not clinically significant, and abnormal clinically significant) will be provided. As a baseline the last assessment before the first day of MDV3100 intake from the prior study will be used.

ECG data will be provided in a data listing.

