7.7 Other Analyses

The Eastern Cooperative Oncology Group (ECOG) scale categorized as grade scores 0-5 will be used to assess performance status. The higher grade score of ECOG indicates the worse of the patient's performance. Number and percentage of subjects with grade scores 0-5 will be tabulated at scheduled visits. A shift analysis table showing shifts from baseline to each scheduled visit in ECOG PS grade will be provided. In addition a shift analysis table showing shift from baseline to the highest ECOG PS grade during the extension study will be provided. As a baseline the last assessment before the first day of MDV3100 intake from the prior study will be used.

The ECOG performance status will be provided in a data listing

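### Laboratory values, ECG and vital signs other than weight are tabulated by visit only, so no table after entry counts how many SAF subjects were ever abnormal; add worst on-treatment summaries

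*SAP*

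**What the plan says.** Long-term safety is the only objective (Protocol 2.1). Vital signs, ECG and laboratory data are three of the five primary safety measures in Protocol 2.3.1.

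- **Vital signs (SAP 7.5.4):** "Descriptive statistics will be presented for each vital sign measurement at each visit", with change from baseline. Weight also gets a categorical table: "In addition for weight a frequency table indicating percentage change from baseline by category* will be provided". No time point is given for it, and the remaining categories are left to TLF specifications that were not supplied.
- **Laboratory (SAP 7.5.2):** "Clinical laboratory evaluations (including hematology and serum chemistry) will be summarized for each visit using descriptive statistics". The shift tables follow the same pattern: "Shift analysis tables will present shift from baseline to the same visits using the NCI-CTCAE grade and laboratory reference range indicator". For ALT or AST, bilirubin and creatinine there is a threshold output, but it is a listing: "In addition a listing will be presented with the indicated subset of laboratory parameters, if at least one of the following criteria is fulfilled".
- **ECG (SAP 7.5.5):** "Overall ECG interpretation will be summarized for each visit", with a shift from baseline to each visit.
- **ECOG (SAP 7.7):** besides the by-visit tables, "a shift analysis table showing shift from baseline to the highest ECOG PS grade during the extension study will be provided".

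SAP 7.1 defines the descriptive statistics for continuous variables as n, mean, SD, median, minimum and maximum. SAP 7.9.1 imputes partial dates only. SAP 7.2.1 notes that the extension has no maximum duration. Under Protocol 3.4, subjects come off drug when "continued administration of study drug is deemed to be not in the subject's best interest by the investigator".

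**The concern.** A by-visit table is a valid description of the subjects seen at that visit. It does not say how many subjects had an abnormal value at any time, because each row has its own denominator and the rows cannot be added. The gap widens with follow-up. Later rows rest on fewer subjects, and who remains depends partly on clinical judgement of how each subject is doing. Reporting change within subject does not remove this, because the set of subjects contributing a change differs from visit to visit.

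Blood pressure shows the practical loss. Hypertension is among the common adverse reactions named in Protocol 1.3, yet the plan has no count of subjects with raised pressure. The by-visit maximum shows one extreme subject, not how many were raised. For laboratory grades and ECG interpretation, a subject who was abnormal once and then left appears in one row only.

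At stake is the plainest long-term safety statement for three primary measures: the number and percentage of subjects who were ever abnormal on treatment.

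**Working it through.** The documents state no sample size, dropout rate or abnormality rate, so there is no figure to reproduce. The check has four parts.

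**1. Which measures have a whole-extension summary table.**

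| Measure | By-visit table | Worst or any-time table |
|---|---|---|
| Laboratory (SAP 7.5.2) | yes, with shifts | none; threshold listing only |
| ECG (SAP 7.5.5) | yes, with shifts | none |
| Vital signs except weight (SAP 7.5.4) | yes, with change | none |
| Weight (SAP 7.5.4) | yes, with change | category table, time point not stated |
| ECOG (SAP 7.7) | yes, with shifts | yes, highest grade |

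**2. Any-time count against by-visit percentages (illustration).** Visit days come from SAP Table 2: 29, 85, then every 84 days to 589, then 757 and 925. Assumptions of mine:

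- Time to stopping drug is exponential, so the share still on drug at day d is S(d) = 0.5^(d/m), where m is the median in days (months x 30.4375).
- A share q = 30% of subjects who stop are abnormal at their last on-drug visit, and at no other visit.
- Stops are counted to Day 925.

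Among subjects with a Week 5 value, ever abnormal = q x [S(29) - S(925)] / S(29). Abnormal at a visit on day d = q x [1 - S(next visit)/S(d)].

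For a 12-month median (365.25 days):

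- Ever abnormal: 0.30 x (94.6 - 17.3)/94.6 = 24.5%.
- Week 5 (56 days to the next visit): 0.30 x (1 - 0.5^(56/365.25)) = 3.0%.
- Visits 84 days before the next: 0.30 x (1 - 0.5^(84/365.25)) = 4.4%.
- Visits 168 days before the next: 0.30 x (1 - 0.5^(168/365.25)) = 8.2%.

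| Assumed median on drug | Still on drug, Weeks 25 / 49 / 85 / 133 | Ever abnormal | Week 5 | Weeks 13 to 73 | Weeks 85 and 109 |
|---|---|---|---|---|---|
| 6 months | 53 / 28 / 11 / 3% | 29.0% | 5.7% | 8.2% | 14.1% |
| 12 months | 73 / 53 / 33 / 17% | 24.5% | 3.0% | 4.4% | 8.2% |
| 24 months | 85 / 73 / 57 / 42% | 17.2% | 1.6% | 2.3% | 4.4% |

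With q = 10%, every abnormality figure is one third of that shown. Abnormalities that persist over several visits would narrow the gap.

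**3. Why a mean hides a subgroup.** If 5% to 10% of subjects rise by 30 mmHg and the rest do not change, the mean moves by 0.05 x 30 = 1.5 to 0.10 x 30 = 3 mmHg.

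**4. Can the selection effect be sized, and would a last on-treatment value correct it?** Weight model, all inputs assumed: mean slope -2% per year, visit noise SD 2%, stopping hazard 0.4 per year multiplied by exp(0.1 per 1% lost). Had everyone stayed, the Week 133 mean would be -2 x 924/365.25 = -5.1%. The simulated by-visit mean at Week 133 depends on the assumed between-subject SD of the slope. Each range below covers a hazard driven by cumulative loss or by slope:

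- SD 4% per year: about -0.5% to +0.8%.
- SD 2% per year: -3.3% to -3.8%.
- SD 1% per year: -4.6% to -4.8%.

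If stopping is unrelated to weight, the by-visit mean is right at about -5.1%, but the mean last on-treatment value is -3.1%, because it pools short and long follow-up. At SD 2% with a hazard driven by cumulative loss, the last on-treatment mean is -2.6%. That is further from -5.1% than the by-visit -3.3%.

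**The case against.** The study is descriptive, and by-visit tables are a legitimate description. Much of what a reader needs is already planned: n at every visit, minimum and maximum (SAP 7.1), disposition by reason (SAP 7.2.1), full listings, and adverse event tables on the whole SAF. Clinically significant laboratory values go into those adverse event tables. So does any test abnormality that causes symptoms, needs intervention, leads to interruption or stopping of drug, or is judged clinically significant (Protocol 5.5.1). Subjects who stop also have a safety follow-up visit with the same assessments, apart from those who withdraw consent or roll over (Protocol 3.4).

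Most of this stands, and it rules out several stronger readings:

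- A reader might infer that no table covers the whole SAF. The adverse event tables do, and Day 1 covers essentially all of it. The gap is in summary tables after entry for the measures named here.
- A reader might infer that late tables show only subjects doing well. They show subjects still attending, including those at their last visit before stopping.
- A reader might infer that weight is also by visit only. The SAP does not say so; it leaves the time point of the category table open.
- A reader might infer a known bias in late means. No rates are given, and part of the late loss may be administrative, because the sponsor is closing the study and offering rollover.

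The missing count survives these points. The adverse event route depends largely on the investigator's judgement, listings are not counts, and follow-up values are taken off drug with no window of their own in SAP Table 2.

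**Conclusion.** The point holds as a gap in the summary tables. For laboratory values, ECG and vital signs other than weight, the plan cannot report from a table how many SAF subjects were ever abnormal on treatment, while SAP 7.7 does so for ECOG, which is not among the primary measures in Protocol 2.3.1.

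This rests on the SAP text alone; the TLF specifications were not available and could already contain such tables. The size is not computable from the documents. In the illustration, any-time figures of 17% to 29% sit beside single-visit figures of 1.6% to 14.1%, under assumed stopping and abnormality rates and with abnormalities seen only once. The weight model shows that selection can distort late means, but the result turns on the assumed slope SD. It supports no claim about this trial's data, and it shows that a last on-treatment row is not a correction for dropout.

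**What to change.** Before the SAP is final:

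1. **SAP 7.5.2:** add shift tables from baseline to the worst on-treatment CTCAE grade and to the worst reference-range flag, with low and high directions separate where both apply.
2. **SAP 7.5.5:** add a shift table from baseline to the worst on-treatment ECG interpretation.
3. **SAP 7.5.4:** add the number and percentage of subjects whose worst on-treatment blood pressure passes a cut-off fixed in the SAP. State that the weight category table uses the worst on-treatment change.
4. **Definitions:** define on-treatment as after Day 1 up to the last MDV3100 dose, and take the worst over all values in that period, because SAP 7.9.2 keeps only one observation per window. Use SAF subjects with a post-Day 1 value as denominator, and print that number as a share of the SAF.

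Keep the by-visit tables. Do not present a last on-treatment row as an adjustment for dropout. The cost is SAP wording and a few more table rows from data already collected at every visit.

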7.5.5 Electrocardiogram (ECG)

Overall ECG interpretation will be summarized for each visit. A shift analysis table showing shifts from baseline to each visit in overall ECG interpretation (normal, abnormal not clinically significant, and abnormal clinically significant) will be provided. As a baseline the last assessment before the first day of MDV3100 intake from the prior study will be used.

ECG data will be provided in a data listing.

7.6 Analysis of Pharmacokinetics

Not applicable.

7.7 Other Analyses

The Eastern Cooperative Oncology Group (ECOG) scale categorized as grade scores 0-5 will be used to assess performance status. The higher grade score of ECOG indicates the worse of the patient's performance. Number and percentage of subjects with grade scores 0-5 will be tabulated at scheduled visits. A shift analysis table showing shifts from baseline to each scheduled visit in ECOG PS grade will be provided. In addition a shift analysis table showing shift from baseline to the highest ECOG PS grade during the extension study will be provided. As a baseline the last assessment before the first day of MDV3100 intake from the prior study will be used.

The ECOG performance status will be provided in a data listing

7.8 Interim Analysis (and Early Discontinuation of the Clinical Study)

Not applicable

7.9 Handling of Missing Data, Outliers, Visit Windows, and Other Information

7.9.1 Missing Data

As a general principle, no imputations of missing data will be done. Exceptions are the following:

- Partially missing date of initial diagnosis will be imputed to get the duration of prostate cancer. For an incomplete initial diagnosis date, the first day of the month and/or the 1st month of the year will be used.
- The worst case scenario will be used in the estimation of partial dates for adverse events and concomitant medication. That is, for an incomplete start date the first day of the month or the first month of the year will be used (unless this leads to an estimated date before the date of first dose of study drug, which will be used in these cases) and for an incomplete stop date the last day of the month or the last month of the year will be used in order to assess whether an adverse event should be analyzed

as a TEAE or whether a medication should be analyzed as concomitant medication. Completely missing start or stop dates will not be estimated. Adverse events or medications with completely missing start date will be assumed to be non TEAEs or not concomitant, respectively. Any stop date that is derived to be after death date or last observed date in the study (e.g. date of lost to follow up) will be set to the date of death or last observed date, respectively. The corresponding listings will always show the original date and time information.

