2.2 Study Design and Dose Rationale

2.2.1 Study Design

This is a multi-center phase 2, open-label extension study in prostate cancer subjects who have completed MDV3100 treatment in a prior MDV3100 study. In order to participate in this study, the subjects must have completed the prior study with MDV 3100, be in the state of at least stable disease and in the opinion of the investigator would derive benefit from continuing MDV3100 treatment. The final visit in the prior MDV3100 study, in which the subject is taking study drug, will serve as the initial visit for this extension study.

This protocol's baseline, for comparison purposes, will be considered the original baseline from the previous MDV3100 study. In addition, all ongoing concomitant medications and AEs from the previous study will be transferred onto the appropriate case report forms (eCRFs) for this study.

All subjects will take 160 mg (4 capsules) MDV3100 once daily oral dose at the same time each day. MDV3100 can be taken with or without food.

Subjects will be discontinued from study drug when continued administration of study drug is deemed to be not in the subject's best interest by the investigator based on clinical assessments. Use of other investigational drugs will also lead to discontinuation.

Throughout the study, safety and tolerability will be assessed by the recording of AEs, monitoring of vital signs and physical examinations, safety laboratory evaluations, and 12-lead electrocardiograms (ECGs).

Subjects that have not met any of the discontinuation criteria as outlined in Section 3.4 may be eligible to continue to receive treatment with enzalutamide in Study [REDACTED] upon approval and activation of this study at the participating institution. Subjects who enroll in Study [REDACTED] will not be required to have a safety follow-up visit.

Subjects who choose not to participate or are not eligible for Study [REDACTED] will complete their participation in Study 9785-CL-0121 by completing the safety follow-up visit upon activation of Study [REDACTED] at the institution.

See Section V, [Table 1](#), Schedule of Assessments for an outline of study procedures.

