3.4 Transfer of data from prior study

Relevant data from the prior study has been transcribed to the eCRF of this study. This is done on the basis of specific instructions by the Investigators involved.

Demographic information (date of birth, ethnicity, race as described by the subject and height) collected at screening of the prior study with MDV3100 has been transcribed onto the appropriate eCRF for this study.

Medical history, as well as non prostate cancer medical history that stopped at or prior to screening, recorded at screening of the prior study with MDV3100 has been transcribed onto the appropriate eCRF for this study.

Medical history and disease history of the target disease recorded at screening of the prior study with MDV3100 has been transcribed onto the appropriate eCRF for this study.

As stated earlier, in addition, all ongoing concomitant medications (including non-medication therapies) and AEs from the prior study have been transferred onto the appropriate case report forms (eCRFs) for this study.

Further details can be found in the Investigators EDC Instruction Manual (see references).

Because of the transfer of all relevant data from the prior study, the reporting of the extension study will be exclusively based on the data available in the database of this extension study. The only exception is that for a number of safety assessments (Laboratory data, Vital signs, ECG data and the ECOG scale) as baseline the last assessment before the first MDV3100 intake of the prior study will be used.

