6.2 Safety Variables

Safety will be assessed by evaluation of the following variables:

- Treatment-emergent adverse events (TEAEs; frequency, seriousness, severity (NCI-CTCAE grade) and relationship to study drug)
- Safety laboratory variables (hematology and biochemistry)
- Vital signs (blood pressure, pulse rate, respiration rate, temperature and body weight)
- Physical examination
- 12-lead electrocardiogram (ECG)

TEAE: An adverse event observed after starting administration of study drug during the extension study. If a subject experiences an event during the prior study with MDV3100 which continues during this extension study, the event will be considered as TEAE only if it has worsened in severity (i.e. it is reported with a new start date during the extension period) All adverse events collected that begin within 30 days of taking the last dose of study drug will also be counted as TEAE.

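### SAP 7.9.1 gives partially dated adverse events carried over from the prior study a start date in the extension, and nothing says whether SAP 6.2 then keeps them out of the TEAE tables

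*SAP*

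**What the plan says.** SAP 7.9.1 states its aim: "The worst case scenario will be used in the estimation of partial dates for adverse events and concomitant medication". The rule is that "for an incomplete start date the first day of the month or the first month of the year will be used", with the exception "unless this leads to an estimated date before the date of first dose of study drug, which will be used in these cases". The section says these estimated dates serve to classify events as TEAEs. A start date that is missing altogether is not estimated, and the event is taken as not treatment-emergent. Listings show the date as recorded.

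SAP 6.2 defines a TEAE as "An adverse event observed after starting administration of study drug during the extension study". For an event that began in the prior study and continues, it adds: "the event will be considered as TEAE only if it has worsened in severity (i.e. it is reported with a new start date", with the parenthesis going on to place that date in the extension period.

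Both documents put carried-over events in the extension database. Protocol 2.2.1 says that "all ongoing concomitant medications and AEs from the previous study will be transferred", and SAP 3.4 confirms that "AEs from the prior study have been transferred onto the appropriate case report forms". SAP 3.4 also bases reporting on this database alone, apart from baseline values for laboratory tests, vital signs, ECG and ECOG. Protocol 7.9.1 leaves imputation to the SAP.

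**The concern.** Moving an early estimate up to the first dose is a sensible worst case in a stand-alone trial, where an event dated only to a month or year might have begun on treatment. In this extension the database also holds events that certainly began earlier. For those, the known month or year can rule out onset in the extension, yet the rule replaces it with the first-dose date.

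That date then meets a TEAE definition in which a start date in the extension is the sign of worsening. SAP 7.9.1 does not exempt carried-over events, does not refer to 6.2 and sets no order between the two. Two programmers could each follow the SAP and produce different TEAE tables.

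TEAEs are the first-listed safety variable, and long-term safety is the only objective. Old, unchanged toxicity could appear in the summaries as new events with onset on Day 1.

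The ordering is also odd. An event with no start date is never a TEAE, while one known to have begun before the extension may be.

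**Working it through.** The plan gives no figure to reproduce: the study is descriptive and has no calculated sample size. The check applies the date rule to examples.

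**Inputs.** The imputation and its floor come from SAP 7.9.1, the TEAE definition from SAP 6.2, and the presence of carried-over events from SAP 3.4 and Protocol 2.2.1. Two dates are assumed for illustration: first prior-study dose 3 Oct 2011 and first extension dose 16 May 2012.

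**Rule as written.** Imputed start = the later of (a) the first day of the known month, or 1 January of the known year, and (b) the first-dose date. An event passes a date-based TEAE test if the imputed start is on or after 16 May 2012. Onset on the dose date must count, or the floor would not be a worst case.

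**Rule with a compatibility condition.** If the latest date the partial date allows is before 16 May 2012, keep (a). Otherwise take the later of (a) and 16 May 2012.

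| Known part of start date | Latest possible start | As written, floor = extension dose | As written, floor = prior-study dose | With compatibility condition |
|---|---|---|---|---|
| Nov 2011 | 30 Nov 2011 | 16 May 2012, passes | 1 Nov 2011, fails | 1 Nov 2011, fails |
| Apr 2012 | 30 Apr 2012 | 16 May 2012, passes | 1 Apr 2012, fails | 1 Apr 2012, fails |
| 2011 only | 31 Dec 2011 | 16 May 2012, passes | 3 Oct 2011, fails | 1 Jan 2011, fails |
| May 2012 | 31 May 2012 | 16 May 2012, passes | 1 May 2012, fails | 16 May 2012, passes |
| 2012 only | 31 Dec 2012 | 16 May 2012, passes | 1 Jan 2012, fails | 16 May 2012, passes |
| Jun 2012 | 30 Jun 2012 | 1 Jun 2012, passes | 1 Jun 2012, passes | 1 Jun 2012, passes |

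The first three rows cannot be extension onsets. With the extension dose as floor, all three are given one. Across the seven months from Oct 2011 to Apr 2012, 7 of 7 are moved to the first extension dose. With the condition, 0 of 7 are moved, and the worst case is kept for May 2012 and for 2012 alone.

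**Whether a moved event becomes a TEAE.** This depends on how 6.2 is applied:

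- If the start-date test uses the imputed date, the event passes whether or not it worsened.
- If it uses the reported date, an unworsened event has no new start in the extension and stays out.

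**Which first dose.** SAP 7.9.1 does not name the study. The fourth column shows the effect of taking the prior-study dose: no old event is moved, but events dated only to May 2012 or only to 2012 fall before Day 1 and fail the test, which defeats the stated worst case.

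**The case against.** A reader might infer that old ongoing events do become TEAEs under this plan. The documents do not establish that. SAP 6.2 speaks of an event being reported with a new start date, and an imputed date is not a reported one. It is also the specific rule for continuing events, while 7.9.1 is a general rule for partial dates. Read that way, an unworsened carried-over event stays out whatever date it is given. This stands as a fair reading, but the SAP does not require it: 7.9.1 says its estimated dates decide TEAE status and makes no exception.

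A reader might also infer that true early extension events are lost. That needs the prior-study reading of the first dose, which is the less natural one. The analysis set (SAP 5.1), the TEAE definition (SAP 6.2) and exposure (SAP 7.3) are all tied to dosing in the extension, and the SAP names prior-study intake elsewhere when it means it. The missing study name is therefore a secondary point.

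Three further limits stand:

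- Protocol 5.5.1 asks for the date and time of onset of each event, so partial dates may be few. The completeness of dates in the prior studies is not given.
- SAP 3.4 refers to an EDC instruction manual, not available here, which may say how carried-over events are identified.
- The analysis is descriptive and the listings keep recorded dates, so a misclassified event could be traced there, though not seen in the summary tables.

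**Conclusion.** The point holds as a conflict between two SAP rules. As written, and with the first dose read as the extension dose, 7.9.1 produces a start date that contradicts known data for every carried-over event whose partial date lies wholly before the extension. Whether such an event is then counted as a TEAE is unsettled, because 7.9.1 points one way, 6.2 can be read the other way, and no precedence is given.

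The size cannot be calculated. Complete start dates are untouched, and wholly missing ones lead to exclusion. The documents give neither the number of subjects nor the share of partial dates, so the count could be anything from none to all transferred events with such partial dates. The 7 of 7 result describes how the rule behaves under the assumed dates; it does not estimate frequency.

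The correction is worth making because it concerns the main safety variable and costs very little.

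**What to change.** In SAP 7.9.1:

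1. Name the reference date as the first MDV3100 dose in study 9785-CL-0121.
2. Use that date as the imputed start only when the known date parts are compatible with onset on or after it. If they lie wholly before it, keep the pre-extension date and treat the event as carried over.
3. State that the worsening rule in SAP 6.2 takes precedence for carried-over events and is applied to reported, not imputed, start dates.

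Item 3 is needed as well as item 2. A carried-over event dated only to the month or year of the first extension dose still satisfies the compatibility condition, and only the precedence rule keeps it out if it has not worsened.

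The cost is a few sentences in the SAP and one programming condition, with no new data. It should be settled before the SAP is signed and the database hard-locked.
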